## 5.6 Study Cohort

The cohort of cladribine-treated subjects will consist of all subjects who have consented to participate and who were treated with cladribine during the clinical trial period of the identified clinical trials or cladribine extension studies in MS.

There will be no control/comparison group. Subjects who were on placebo during a clinical trial but who switched to cladribine in the extension study will contribute person-time to the cohort of cladribine-treated subjects from the moment they initiate cladribine. Person-time prior to cladribine initiation in subjects originally randomized to placebo, will not be used in the calculation of study endpoints incidences.

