## **7 Assessment of Medication Exposure**

After enrollment of subjects in the registry, in accordance with the non-experimental nature of this study, no treatment will be assigned to participants by registry protocol. Physicians will prescribe medications according to their own clinical criteria and practices. Information regarding use of marketed immunosuppressant medications will be collected during the registry.

Subjects will no longer be eligible to participate in PREMIERE if they enroll in an interventional clinical trial, as it may not be possible to know medication exposure.

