6.2 Final Analysis

All final, planned analyses identified in the Clinical Study Protocol and in this IAP will be performed only after the last participant has completed the study (following protocol definition) with all study data in-house, all data queries resolved as much as possible, and the database locked.

7 Changes to the Planned Analyses in the Clinical Study Protocol

As usual, Statistical Analysis Plans are more detailed than relevant sections of the Study Protocols; such additions and refinements are therefore not mentioned in this section. Instead, only true deviations from statements in the study protocol are listed together with a brief rationale.

Table 1 Changes from the planned analyses in the clinical study protocol

Protocol Section: Item	Protocol definition	Changes implemented in the SAP
Section 5.6: Study Cohort	There will be no control/comparison group	"Never exposed to Cladribine" group will be considered as reference for a long-term non-treated population.

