9.1 Treatment groups

Analyses will be performed on the "as treated principle", where patients are allocated to the treatment group that they actually received in the clinical trial studies (which may be different from the study treatment to which they were randomized to).

Patients are assigned to the following treatment groups according to their actual treatment in one of the studies CLARITY alone, ONWARD, CLARITY/CLARITY EXTENSION, ORACLE MS, Pantoprazole DDI.

- **Never exposed to cladribine:** if a subject has taken only placebo (or placebo +IFN-β) in studies, then her/his data becomes part of the "Never exposed to cladribine" treatment group. A subject who switches treatment from placebo to cladribine in subsequent studies/periods **will not** be considered in this group.
- **Exposed to cladribine:** patients with at least one dose of cladribine. Subjects who were on placebo during the clinical trial and switched to cladribine in the extension study will contribute to the treatment group "Exposed to cladribine" from the moment they initiate cladribine.

An example of the header for table outputs is presented below.

Table 2 Table header example

	Never exposed to Cladribine (N=XXXX)	Exposed to Cladribine (N=XXXX)	Total (N=XXXX)
Safety Analysis Population	xxx (100.0)	xxx (100.0)	xxx (100.0)

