11.2 Medical History

No reporting will be done.

12 Previous Medications or Medications/Procedures in PREMIERE

Medications in PREMIERE will be presented by Category, Therapeutic group (ATC level 2) and Preferred Name, per treatment group and total, using crude incidence:

Crude incidence, in % = (number of subjects with at least one medication / total number of subjects) * 100.

The following categories as reported in the CRF will be presented:

- MS-Related Immunomodulators and Immunosuppressants
programming note CM.CMSPID = 101-199
- MS-Related Symptomatic Medications, including pain control
programming note CM.CMSPID = 201-299
- MS-Related Antidepressants
programming note CM.CMSPID = 301-399
- OTHER MS- AND NON-MS-RELATED
programming note CM.CMSPID = 401-499

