12.2.1 Disease Modifying Drugs in PREMIERE

MS-disease modifying drugs (DMDs) drugs are defined by **custom selection** based on all concomitant medication collected.

Table 5 List of MS-DMD

Preferred Term (WHODD)
ALEMTUZUMAB
BETASERON /01229701/
DIMETHYL FUMARATE
FINGOLIMOD
FINGOLIMOD HYDROCHLORIDE
FUMARIC ACID
GLATIRAMER ACETATE
INTERFERON BETA
INTERFERON BETA-1A
INTERFERON BETA-1B
MITOXANTRONE
MITOXANTRONE HYDROCHLORIDE
NATALIZUMAB
PEGINTERFERON BETA-1A
RITUXIMAB
TERIFLUNOMIDE

Note: the final list of medications may be revised after database lock. Any changes from the list above will be described in the CSR.

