15.1 Primary Endpoints

15.1.1 Serious Adverse Events Related to Cladribine

Reporting will be done for SAF.

The objective is “to quantify and characterize the risk (cumulative incidence) of SADR, including malignancies and serious infections”.

Definition

The primary endpoint will be selected considering any serious adverse event characterized as Probable or Possible in the relationship to cladribine. Malignancies and serious infections will be considered in this endpoint only if the characteristics “serious” and “related” (“probable” or “possible”) are applicable.

Following protocol section 8.5.1.2, “an adverse drug reaction (ADR) is a response to a medicinal product which is noxious and unintended, and which occurs at doses normally used in man for prophylaxis, diagnosis, or therapy of disease or for the restoration, correction, or modification or physiological functions. Response in this context means that a causal relationship between a medicinal product and an adverse event is at least a reasonable possibility”.

The treating physician or other relevant concerned health care provider are asked to assess the relationship of the AEs to cladribine using the following definition, similar in all studies:

- Probable: A causal relationship is clinically/biologically highly plausible, and there is a correlation between the onset of the SAE and administration of cladribine, and between withdrawal of cladribine and resolution of the SAE.

- Possible: A causal relationship is clinically/biologically plausible and there is a correlation between the onset of the SAE and administration of cladribine.
- Unlikely: A causal relationship is improbable, and another documented cause of the SAE is most plausible.
- Unrelated: A causal relationship can be definitively excluded, and another documented cause of the SAE is most plausible.

The following statistics will be presented:

- Patient-year is the sum of the time since the end of clinical trial, expressed in years. Display with 1 decimal.
- m is the number of unique events. A unique event is a unique Preferred Term and date of onset per subject.
- n is the number of subjects with at least one event
- N is the total number of subjects in the treatment group
- AE (%) is the crude incidence. Display with 1 decimal.
 - $AE(\%) = (\text{number of subjects with at least one event} / \text{total number of subjects}) * 100$

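### SAP Table 1 describes the never-exposed group as non-treated, yet its subjects may have had IFN-β and later MS drugs, and no adverse-event table separates time after a later drug was started

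*SAP*

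**What the plan says.** Protocol 5.6 is explicit: "There will be no control/comparison group". SAP section 7, Table 1 lists a departure from that section, under which the never-exposed "group will be considered as reference for a long-term non-treated population".

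SAP 9.1 sets the membership rule. A subject belongs to the group "if a subject has taken only placebo (or placebo +IFN-β) in studies". The test is the absence of cladribine in the source trials, not the absence of other treatment.

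For the period after the trials, Protocol section 7 says "Physicians will prescribe medications according to their own clinical criteria and practices". The one limit it sets is that "Subjects will no longer be eligible to participate in PREMIERE if they enroll in an interventional clinical trial". SAP 12.2.1 (Table 5) lists 16 MS disease-modifying drug terms to be identified, including alemtuzumab, fingolimod, mitoxantrone, natalizumab, rituximab and the interferons.

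SAP section 12 provides a medication table: "Medications in PREMIERE will be presented by Category, Therapeutic group (ATC level 2) and Preferred Name, per treatment group and total". It uses crude incidence, that is, subjects with at least one record over all subjects.

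The adverse-event tables cover all time from the day after the trial ended to the last registry date (SAP 9.2). Their person-time follows the same window: "Patient-year is the sum of the time since the end of clinical trial, expressed in years".

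**The concern.** The label and the membership rule disagree. A group that admits IFN-β during the trial and any prescribed MS drug afterwards is not an untreated population. Calling it a reference invites the reader to take its column as background risk for infections, neoplasms and blood disorders in untreated MS.

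Several of the Table 5 drugs act on the immune system, so they may bear on the same outcomes. If never-exposed subjects start such drugs sooner or more often, the background shown could be raised. If exposed subjects do, their column could be raised instead. An ever-use table can show unequal uptake, but it cannot show whether a given infection or neoplasm came before or after the drug.

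The tables will also travel. SAP section 4 foresees their use in regulatory submissions and manuscripts, and SAP 15.3.1 and 15.3.2 specify per-group event tables for the public registries.

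**Working it through.** There is no plan figure to reproduce: the cohort is not sized by sample-size methods (Protocol 9.1), and no contrast between the groups is specified. The check is a reading of each table specification for any handling of later drugs.

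| SAP section | Content | Shown by | Handling of later MS drugs |
|---|---|---|---|
| 12, 12.2 | Medications in the registry | Group and total | Ever-use only, not linked to events |
| 15.1.1 | Serious adverse drug reactions | Group and total | None, but limited to events judged probably or possibly related to cladribine |
| 15.1.2 | Blood and lymphatic disorders | Group and total | None |
| 15.1.3 | Neoplasms | Group and total | None |
| 15.1.4 | Lymphocyte grades, lymphopenia | Group and total | Best and worst grade taken from the first such drug onwards; use before resolution shown |
| 15.3, 15.4 | All events, serious events, deaths | Group and total | None |
| 15.5 | Infections, malignancies | Group; summary repeated by source trial | None |

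The SAP thus relates later drugs to an outcome only in 15.1.4. In every other outcome table, events before and after a later drug are pooled within each column. Some lines in SAP 10.1 and 15.5.1 are redacted and could not be checked.

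**Can a direction or size be stated?** As a test, suppose cladribine has no effect, later drugs multiply the event rate by d, and they cover a share f0 of never-exposed time and f1 of exposed time. The ratio of the two rates would then be

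[1 + f1(d − 1)] / [1 + f0(d − 1)].

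All inputs below are assumptions, because the documents give none of them.

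- f0 = 70%, f1 = 30%: d = 1.5 gives 1.15/1.35 = 0.85; d = 3 gives 1.60/2.40 = 0.67.
- f0 = f1 = 30%: the ratio is 1.00 for any d.
- f0 = 30%, f1 = 50%: d = 1.5 gives 1.25/1.15 = 1.09; d = 3 gives 2.00/1.60 = 1.25.

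The sign changes with the assumed uptake. The SAP reports neither this ratio nor a rate: its incidence measure is the proportion of subjects with an event. The arithmetic shows only that direction and size are open. It does not estimate a bias.

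**The case against.** The case on the other side has real weight.

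- **No comparison is estimated.** SAP 9.14 rules out statistical inference, and SAP 15.1.1 gives each group its own crude incidence and exact interval. This stands. A reader might infer that the plan will produce a distorted cladribine effect of some stated percentage, but no such contrast is specified.
- **Non-treated may mean not treated with cladribine.** This is plausible in context, and the table header in SAP 9.1 uses the never-exposed name. The SAP does not say so, however, and a reference group should not depend on a charitable reading.
- **Serious adverse drug reactions are already filtered.** This stands. An event with another documented, more plausible cause should be classed as unlikely or unrelated, which removes it from 15.1.1. The filter is imperfect, but a further split there is not needed.
- **Later drugs are not ignored.** Uptake by group will be visible, and the source-trial repeat in 15.5 may partly isolate IFN-β given in a trial, although the documents do not say which trial used it. Neither shows the order of drug and event, and 15.1.2 and 15.1.3 are not repeated by trial.
- **Grouping by trial exposure regardless of later therapy is legitimate in a registry.** Agreed. The point is that the label should say so.

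**Conclusion.** The point holds as a mislabelled reference and a missing descriptive view. The adverse-event columns compare subjects who had trial cladribine with subjects who did not, each with any therapy prescribed later outside interventional studies.

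A reader might go further and infer that the reference column masks or inflates a cladribine excess. The documents do not support that. They give no uptake by group, no timing and no effect of later drugs on these events, and equal uptake would leave the assumed ratio above unchanged. Direction and size are undetermined.

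The change is worth making because the contradiction lies within the SAP itself, because the SAP already relates later drugs to lymphocyte results, and because drug type and start date are collected at follow-up (Protocol 8.4).

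**What to change.** 1. In SAP Table 1, replace the non-treated description with: *subjects not exposed to cladribine in the source trials (background and later MS drugs permitted)*.
2. For SAP 15.1.2, 15.1.3 and the infection and malignancy events of special interest in 15.5, add one supportive descriptive summary per endpoint, by treatment group. Split events and patient-years into time before, and time on or after, the first post-trial start of a drug in the CRF category for MS-related immunomodulators and immunosuppressants (CMSPID 101-199). Subjects already on such a drug at Registry Day 1 go in the second stratum. This extends the first-start rule in SAP 15.1.4. Leave 15.1.1 as it is.

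The cost is one line of wording and a few tables from dates already collected. State these limits with the tables:

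- Starting a drug is itself prognostic, so the split is descriptive.
- Strata will be sparse.
- The category mixes immunomodulators with immunosuppressants.
- Time after a drug is stopped stays in the second stratum.
- Some ordering will rest on imputed dates. SAP 12.4 moves partial drug starts to the beginning of the month or year, and some fully missing starts to the day before Registry Day 1. SAP 15.6 also moves partial event onsets early.

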### 9.2 Data analysis

#### 9.2.1 General Considerations

The analysis set will consist of all subjects enrolled in the registry at the time of the analysis.

For safety analyses, subjects will be analyzed according to their actual exposure to oral cladribine.

Life table analysis is the traditional method for evaluating the mortality/morbidity of a fixed population that is followed for a period of time, and the frequency of the events are evaluated at predefined time intervals. Commonly, if effects exist, they are most likely not constant over time, and the life table methodology elucidates the time dependence of the events in relation to the onset of an exposure. The most important aspect of the life table method is the incorporation in the survival analysis of the duration of the time taken to reach the outcome event [10, 11, 12].

Therefore, the main analysis will be to estimate cumulative incidence rates using life-table methodology.

---

 Reporting requirements for cases derived from observational (noninterventional) post-authorisation safety studies sponsored by the pharmaceutical industry are laid down in *Volume 9A of the Rules governing Medicinal Products in the European Union – Guidelines on Pharmacovigilance for Medicinal Products for Human Use*. However, it is unclear how Volume 9A guidance applies in a preapproval situation. Volume 10 only applies to clinical trials.

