TLF	Tables, Listings, and Figures
WHO-DD	World Health Organization Drug Dictionary

3 Modification History

Unique Identifier for Version	Date of IAP Version	Author	Changes from the Previous Version
NA			

4 Purpose of the Integrated Analysis Plan

The purpose of this IAP (integrated analysis plan) is to document technical and detailed statistical specifications for the final analysis of data collected for protocol EMR700568-012 called PREMIERE. Results of the analyses described in this IAP will be included in the Clinical Study Report (CSR). Additionally, the planned analyses identified in this IAP will be included in regulatory submissions or future manuscripts. Any post-hoc, or unplanned analyses performed to provide results for inclusion in the CSR but not identified in this prospective IAP will be clearly identified in the CSR.

The IAP is based upon section 9 (Data Analysis and Statistics) of the study protocol and protocol amendments and is prepared in compliance with International Conference on Harmonization (ICH) E9 and Guidelines for Good Pharmacoepidemiology Practices (GPP). It describes analyses planned in the protocol and protocol amendments.

5 Objectives and Endpoints

Objectives	Endpoints (Outcome Measures)	Endpoints (Outcome Measures) Timeframe	IAP section
Primary			

 To quantify and characterize the risk (cumulative incidence) of serious adverse drug reaction (SADR), including malignancies and serious infections To assess time to resolution of lymphopenia among registry participants with persistent lymphopenia To quantify and characterize the risk (cumulative incidence) of AE in the 'Blood and Lymphatic System Disorders' and 'Neoplasms Benign, Malignant, and Unspecified' System Organ Classes (SOCs) 	
 Cumulative incidence of SADR, including malignancies and serious infections Time to resolution of lymphopenia, among registry participants with persistent lymphopenia Cumulative incidence of all AEs in the "Blood and Lymphatic System Disorders" System Organ Class (SOC) and in the "Neoplasms Benign, Malignant, and Unspecified" SOC 	
 AE crude incidence from Registry Day 1 to End of registry Time to resolution of lymphopenia, for participants with ongoing lymphopenia at the end of clinical trial AE crude incidence from Registry Day 1 to End of registry 	
 Section 15.1.1 Section 15.1.4 Section 15.1.2 & 15.1.3

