Section 9.2.2 Treatment/Analysis periods	Demographic characteristics (e.g., age, sex) at baseline of the registry will be described using descriptive statistics for continuous variables or proportions for categorical variables at entry into the registry. Summaries will be provided by region/country.	Demographic characteristics will not be summarized by region/country. Instead, based on the understanding of the protocol, summary statistics for the number of subjects by country will be provided.
Section 9.2.1 General Considerations	Time to resolution of persistent lymphopenia will be estimated using the life table methodology.	
The time to resolution of lymphopenia (duration of lymphopenia episode) has already been presented in the ISS using the product-limit method of Kaplan and Meier. This analysis will not be repeated.
 
The time to resolution of lymphopenia for participants with ongoing lymphopenia at end of clinical trial will be analyzed using descriptive statistics.

Section 9.2.1 General Considerations	The main analysis will be to estimate cumulative incidence rates using life-table methodology.	
The main analysis of adverse events will be done on the period from the end of clinical trial + 1 day to the last date in PREMIERE registry. The life-table methodology will not be used. Rather, the crude incidence will be presented with the corresponding 95% confidence interval.
 
The time to first event from the first dose of cladribine has already been presented in the ISS following the Kaplan-Meier methodology for AESI infections and malignancies. Therefore, it will not be repeated here.

Section 10.2 Subject information and informed consent	Subjects who refuse to enroll in the registry will be asked to sign consent (see CRF: Data Release Participant only) for use of their clinical trial data to compare registry non-participants with registry participants in terms of demographics, cancer risk factors and severity of MS.	Comparison of registry participant's vs non-registry participants will not be performed due to very strong sample size imbalance between the 2 groups. Indeed as the registry target population was of 2175 subjects, 1161 patients enrolled as full participants and 22 refused and signed the data release consent form only.
---	---	---

8 Protocol Deviations and Analysis Populations

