9.14 Significance level

There are no plans for any statistical inference. This study will adhere to the Guidelines for Good Pharmacoepidemiology Practices (GPP). Accordingly, data evaluations and interpretations will be based on point estimates and 95% confidence intervals (CI) for the evaluation of the statistical precision around the point estimate.

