- 95% Confidence Interval (CI) for the crude incidence within group for patients with at least one AE. The 95% Confidence Interval of the AE will be computed using the exact Clopper-Pearson confidence interval formula for binomial proportions (REF. Clopper item #3).

Statistics description

The following statistics per treatment group and total will be presented:

- Summary: Patient-years will be provided in the summary table. In addition, number of unique event, number of patients with at least one AE, crude incidence (%), 95% CI of the crude incidence. All these statistics will be repeated for AE leading to death and serious AE.

Note: SADR is a serious AE by definition. Therefore, only SADR and SADR leading to death will be presented.

- By SOC/ HLGT/ HLT/PT: Number of patients with the AE and crude incidence (%) will be presented by system organ class (SOC), High Level Group Term (HLGT), High Level Term (HLT), and preferred term (PT).

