15.1.2 Blood and Lymphatic System Disorders

Reporting will be done for SAF.

Any adverse event preferred term belonging to the MedDRA SOC="Blood and Lymphatic System Disorders" will be selected.

Statistics as presented for section 15.1.1, Serious Adverse Events Related to Cladribine, will be repeated.

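### Primary endpoints 1 and 3 are still defined as cumulative incidence, but the SAP estimates them by crude n/N over unequal follow-up, with no time-specific risk and no rate with a confidence interval

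*SAP*

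**What the plan says.** Protocol 9.2.1 sets the main analysis: "Therefore, the main analysis will be to estimate cumulative incidence rates using life-table methodology". Protocol 9.2.2 counts the first occurrence of each endpoint, and 9.3.1 censors subjects who stop responding.

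SAP section 7, Table 1 replaces this: "The life-table methodology will not be used. Rather, the crude incidence will be presented with the corresponding 95% confidence interval". The reason given is that time to first event from first dose was already shown by Kaplan-Meier in the Integrated Summary of Safety (ISS) for infections and malignancies of special interest.

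SAP section 5 keeps the objective and endpoint as cumulative incidence and puts beside them, as timeframe, "AE crude incidence from Registry Day 1 to End of registry". SAP 15.1.1 defines the estimator as subjects with at least one event over all subjects in the group: "AE (%) is the crude incidence. Display with 1 decimal". For its interval, "The 95% Confidence Interval of the AE will be computed using the exact Clopper-Pearson confidence interval formula for binomial proportions". SAP 15.1.2 says "Statistics as presented for section 15.1.1, Serious Adverse Events Related to Cladribine, will be repeated", and 15.1.3 does the same for neoplasms. On follow-up, 15.1.1 says "Patient-years will be provided in the summary table", and 10.1 tabulates time since the end of the trial by group.

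**The concern.** A cumulative incidence is a probability by a given time. The SAP's clock starts the day after the subject's last cladribine trial ended (SAP 9.2, 9.8). Follow-up stops at the end of the registry or 8 years after entry to the subject's first trial, whichever is earlier (protocol 5.7). Under the 8-year cap, each year spent in trials is a year lost from post-trial follow-up. Withdrawal, loss, death and entry into an interventional study (protocol 5.7.1, 5.7.2, 7; SAP 9.9) shorten it further. n/N gives a subject followed for a few months the same weight as one followed for six years, so it averages risks over an unstated mixture of follow-up times.

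Two of the three primary endpoints of a long-term safety registry are affected. SAP 9.14 rests interpretation on point estimates and their 95% intervals, and the only interval specified for these endpoints belongs to n/N. The SAP also adds a never-exposed reference column (Table 1) and counts placebo subjects who switched to cladribine in the extension as exposed (9.1), so time spent in trials may differ between the two columns.

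**Working it through.** The documents give no event count, incidence, loss rate or time in trial for this purpose, so there is no planned figure to reproduce. Every hazard, loss rate, trial duration and extension share below is an assumption.

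**Follow-up caps.** Time available after the trial is 8 − w × 7/365.25 years for w weeks in trials, if the 8-year limit binds. For 96 weeks (single trial) this is 6.16 years; for 192 weeks (core plus extension), 4.32 years.

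**Within one group.** With constant hazard h, constant loss rate d and cap T, expected n/N = h/(h+d) × (1 − exp(−(h+d)T)). Take h = 0.005 and 30% of subjects from the extension. With no loss: 0.7 × 3.03% + 0.3 × 2.14% = 2.76%. The risk at the longest follow-up is 1 − exp(−0.005 × 6.16) = 3.03%. The equivalent time is −ln(1 − n/N)/h.

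| Loss per year | n/N | Equals the true risk at | Below 3.03% by |
|---|---|---|---|
| 0% | 2.76% | 5.61 y | 8.9% |
| 2% | 2.61% | 5.29 y | 13.9% |
| 5% | 2.41% | 4.87 y | 20.7% |
| 10% | 2.11% | 4.26 y | 30.5% |

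The hazard is the same in all four rows.

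**Interval.** In 4,000 simulated registries of 1161 subjects (the number of full participants in SAP Table 1), half capped at 4 and half at 6 years, with 1 event per 100 patient-years, the Clopper-Pearson interval covered the 6-year risk in 75%, 39% and 14% of runs at 0, 5 and 10% annual loss. At 0.3 per 100 patient-years, coverage was 92%, 83% and 70%.

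**Same n/N, different follow-up.** 35/1161 is 3.0% (2.1 to 4.2) whatever the follow-up. Over 1161 × 6 = 6966 patient-years it is 0.50 per 100 (0.35 to 0.70); over 1161 × 4 = 4644 it is 0.75 (0.52 to 1.05).

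**Between groups, equal hazards.** Take 96/192 weeks, all never-exposed subjects from single trials, and 10/30/50% of the exposed from the extension. The crude exposed/never ratio is:

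- no loss: 0.97/0.91/0.85
- loss of 10% per year in never-exposed and 5% in exposed: 1.12/1.06/1.00
- 5% and 2%: 1.06/1.00/0.94
- 5% and 10%: 0.85/0.81/0.77

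Adding a 2%/5% loss pattern and trial-time pairs of 48/144, 96/144 and 96/216 weeks widens the range to 0.74 to 1.15. The sign is open.

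**Does a rate repair it?** Under constant hazard the first-event rate ratio is 1.00 in every cell, but only because the hazard was assumed constant. With equal Weibull hazards scaled to 3% risk at 6.16 years, the 96/192-week grid gives rate ratios of 0.96 to 1.12 for shape 0.5 and 0.83 to 1.03 for shape 2.

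**The cited ISS analysis.** It is named for infections and malignancies of special interest and runs from first dose. It belongs to an ISS that includes subjects not enrolled in PREMIERE and has a cut-off of 15 May 2017, 528 days before last patient last visit on 25 October 2018 (SAP section 6).

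**The case against.** The strongest reply is that this is a disclosed descriptive choice with its denominators shown. Much of that stands. Table 1 declares the deviation, and no planned statistic is called cumulative incidence. No inference or formal contrast is planned. Patient-years, events, subjects and percentages appear by group in one table, and follow-up is summarised by group and by previous trial. The summaries for events of special interest are also repeated by previous trial (SAP 15.5).

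Four stronger readings are tempting, and the documents do not support them:

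- **That the SAP disguises n/N as cumulative incidence.** It does not. The mismatch is between the endpoint and its estimator.
- **That a reader cannot see differences in follow-up.** They are visible, and a rate can be approximated by hand. What is missing is a specified rate with its interval and any risk at a stated time.
- **That the comparison with never-exposed subjects is biased in a known direction.** Extension subjects have less post-trial time, early trial drop-outs more, and differential loss can reverse the sign.
- **That a rate per patient-year is enough.** The Weibull results show otherwise, and protocol 9.2.1 itself expects effects to vary over time.

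The ISS may hold more than Table 1 mentions. That cannot be checked here, but as described the cited analysis is not stated to cover serious adverse drug reactions overall or the Blood and Lymphatic class.

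The remedy also has complications. Enrolment depends on surviving to consent and being reachable, events between trial end and enrolment are collected retrospectively, and prospective collection for endpoint 3 began only on local approval of amendment 1 (protocol 5). Time-based estimates also depend more on imputed onset dates (SAP 15.6) than an ever/never count does.

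**Conclusion.** The point holds and should be fixed. For endpoints 1 and 3 the planned estimator does not deliver the risk named in the objective: n/N has no time point, and its interval is the only one specified. That conclusion follows from the text alone. That n/N understates the risk at the longest follow-up requires only censoring unrelated to risk. The amount, 9% to 30% in the within-group illustration, rests entirely on the assumed hazard, loss, trial durations and extension share. No size or direction can be given for any exposed versus never-exposed distortion. Disclosure and the tabulated patient-years limit the harm without closing the gap.

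**What to change.** On the final database, by treatment group, for endpoints 1 and 3:

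1. Restore a life-table or Kaplan-Meier cumulative incidence of first events (or a competing-risk estimate with death as the competing event) from end of trial + 1 day. Give 95% intervals and numbers at risk at stated times that enough subjects in each group reach.
2. Add, as a companion, the first-event rate per 100 patient-years with an exact Poisson 95% interval, stopping person-time at first event, death or last contact. Note that it removes follow-up differences fully only if the hazard is roughly constant.
3. Keep n/N as a descriptive count.
4. Repeat 1 and 2 with time at risk and events counted from registry consent (delayed entry). For endpoint 3, repeat also from the local start of prospective collection under amendment 1.

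Cost: SAP wording and a few extra programs and tables, with no new subject data. Start date, last date and patient-years are already defined (SAP 9.6, 9.9, 10.1). Two decisions are needed: whether the last date in any dataset (SAP 9.9) can serve as last contact, and how imputed onset dates are flagged, since the new estimates depend on them somewhat more.

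Relative precision of the rate is practically that of n/N. For an assumed 10 first events in 900 subjects followed 4.5 years each (4050 patient-years), n/N is 1.11% (0.53 to 2.03) and the rate is 0.247 per 100 patient-years (0.118 to 0.454). The upper-to-lower limit ratios are 3.81 and 3.84.
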